11.12 Eosinophilic Esophagitis Symptom Score

Symptoms of Eosinophilic Esophagitis range from abdominal pain, gastroesophageal reflux, vomiting, and difficult swallowing. The symptoms will range from none to very severe as in Spergel⁵⁴. The symptoms will be in 3 categories and individual symptoms and total symptoms scores will be collected on a range of 0-4 (0-none, 1-mild, 2-moderate, 3-severe and 4-very severe).

Table 4: Eosinophilic Esophagitis Score

Symptoms	Score
Abdominal/Chest Pain	0-4
Vomiting/Regurgitation	0-4
Dysphagia	0-4
Total Score	0-12

11.13 Skin Reaction and Photography

Skin reactions under the Viaskin® will be graded (ideally by the same site person) at each visit according to the modified recommendations of the EAACI/GA²LEN position paper in Turjanmaa et al (23):

Table 5: Skin Reaction Grading System

Grade	Skin Reaction
Grade 0	Negative
Grade 1	Only erythema, or erythema + infiltration
Grade 2	Erythema, few papules
Grade 3	Erythema, many or spreading papules
Grade 4	Erythema, vesicles

Viaskin® patches are transparent and the degree of local reactions under the Viaskin® can be easily seen. Grades of local skin reactions will be recorded after 3 hours of application for the first day of treatment (V4), after 1 hour of application at Day 8 of treatment (V5) and when subjects arrive for a visit for other protocol visits.

Photographic records will be taken of site(s) of application of the Viaskin® and filed in the subject's medical records or source document in case a further review of local reactions is required.

12. SAFETY MEASUREMENTS AND VARIABLES

12.1 Adverse Events Definition

An AE is any untoward medical occurrence that does not necessarily have a causal relationship with the investigational medicinal product. An AE can therefore be any unfavorable or unintended sign, including an abnormal laboratory finding, symptom or disease temporally associated with the use of an investigational medicinal product whether or not considered related to the investigational medicinal product.

AEs will be monitored throughout the entire study. Investigators will ask the subject at each visit if they have experienced any untoward effects since the last study visit. All AEs will be recorded on the eCRFs provided. A description of the event, severity, time of occurrence, duration, any action

(e.g. treatment and follow up tests) and the outcome should be provided along with the Investigator's assessment of the relationship to the study treatment.

AEs will be recorded from the time written screening informed consent is signed until the time of the End of Study visit. AEs still ongoing at the time of End of study visit will be followed for an additional period to encompass a total period of 14 days of AE follow-up after administration of the last dose of treatment.

If known, the name or diagnosis of the illness should be recorded, rather than a listing of individual signs or symptoms. AEs must be graded as being mild, moderate or severe and their start and end dates given. Definitions of severity are as follows:

- Mild:** an AE usually transient in nature and generally not interfering with normal activities
- Moderate:** an AE that is sufficiently discomforting to interfere with normal activities;
- Severe:** an AE that is incapacitating and prevents normal activities.

Even if the Investigator feels there is no relationship to the study drug, all adverse experiences MUST be recorded in the eCRF. The Investigator is requested to assess the relationship of any clinical adverse experience to treatment using the following definitions:

Unrelated: those AEs which are clearly and incontrovertibly due to extraneous causes (concurrent drugs, environment etc.) and do not meet the criteria for drug relationship listed under Unlikely, Possible, Probable or Related.

Unlikely: an adverse experience may be considered unlikely if it includes at least the first two features:

- It does not follow a reasonable temporal sequence from administration of the drug.
- It could readily have been produced by the subject's clinical state, environmental or toxic factors, or other modes of therapy administered to the subject.
- It does not follow a known pattern to the suspected drug.
- It does not reappear or worsen when the drug is re-administered.

Possible: an adverse experience may be considered possible if it includes at least the first two features:

- It follows a reasonable temporal sequence from administration of the drug.
- It could readily have been produced by the subject's clinical state, environment or toxic factors, or other modes of therapy administered to the subject.
- It follows a known response pattern to the suspected drug.

Probable: an adverse experience may be considered probable if it includes at least the first three features:

- It follows a reasonable temporal sequence from administration of the drug.
- It could not be reasonably explained by the known characteristics of the subject's clinical state, environmental or toxic factors or other modes of therapy administered to the subject.

- It disappears or decreased on cessation or reduction in dose. There are exceptions when an AE does not disappear upon discontinuation of the drug (e.g. bone marrow depression, fixed drug eruptions, tardive dyskinesia, etc).
- It follows a known pattern of response to the suspected drug.

Related: an adverse experience may be considered related if it includes all of the following features:

- It follows a reasonable temporal sequence from administration of the drug.
- It could not be reasonably explained by the known characteristics of the subject's clinical state, environmental or toxic factors or other modes of therapy administered to the subject.
- It disappears or decreased on cessation or reduction in dose. There are exceptions when an AE does not disappear upon discontinuation of the drug. For example: bone marrow depression, fixed drug eruptions, tardive dyskinesia, etc.
- It follows a known pattern of response to the suspected drug.
- It reappears or worsens if the drug is re-administered.

12.2 Serious Adverse Events

A SAE is any untoward medical occurrence or effect that fulfills any of the following criteria:

- results in death;
- is life-threatening;
- requires hospitalization or prolongation of existing in-subject hospitalization;
- results in persistent or significant disability or incapacity;
- is a congenital abnormality/birth defect;
- important medical events not captured by the above but which may, for example, require medical intervention to prevent one of the outcomes above.

Events associated with hospitalization for the following will not be considered as an SAE:

a) Evaluation or treatment of a pre-existing condition and non-exacerbating condition as long as the condition(s) associated with the hospitalization: existed prior to the subject's entry into the study and has been recorded in the subject's medical history as documented in the eCRF (e.g. degenerative disease) has not worsened in severity or frequency during the subject's exposure to study medication has not required a change in treatment management during the subject's exposure to the study medication

b) Treatment which is elective or pre-planned of a pre-existing condition and non-exacerbating condition.

Unanticipated Problems Involving Risk to Subjects or Others:

Any incident, experience, or outcome that meets all of the following criteria:

- Unexpected in nature, severity, or frequency (i.e. not described in study-related documents such as the IRB-approved protocol or consent form, the investigators brochure, etc)
- Related to participation in the research (i.e. related means there is a reasonable possibility that the incident experience, or outcome may have been caused by the procedures involved in the research)

- Suggests that the research places subjects or others at greater risk of harm (including physical, psychological, economic, or social harm).

Unexpected, suspected adverse reaction: A suspected adverse reaction is considered “unexpected” if it is not listed in the general investigational plan, clinical protocol, or elsewhere in the current IND application; or is not listed at the specificity or severity that has been previously observed and/or specified.

12.3 Reporting of Serious Adverse Events, Unanticipated Problems, and Serious Unexpected Suspected adverse reactions

This trial will be conducted under an investigator initiated IND held by [name]. The Principal Investigator will be responsible for the conduct of the trial and adherence to CHOP IRB SOP 408 Unanticipated Problems Involving Risks to Subjects and FDA Regulations 21 CFR 312.32 IND Safety Reporting. This includes but is not limited to collecting, assessing, reporting all adverse experiences, and monitoring/assessing the safety implications of any new pre-clinical, clinical, or manufacturing updates that occur during the course of the study investigation. If the Principal Investigator determines the new information significantly impacts safety they will promptly notify the IRB, FDA, and any other protocol specified safety committee or monitor.

Reporting requirements for SAEs will be managed by the investigator. Full details of the procedures to be adopted will be documented in a safety management plan will be prepared by Westat:

Any AE which occurs in any subject after signing the screening informed consent through the last visit must be reported. All SAEs that occur before the end of study following cessation of the last dose of treatment with the study drug, whether or not considered related to the investigational product must also be reported. All subjects with SAEs must be followed up for outcome.

All SAEs will be reported to the CHOP IRB and FDA per current regulations (CHOP IRB SOP 408 Unanticipated Problems Involving Risks to Subjects and FDA Regulations 21 CFR 312.32 IND Safety Reporting).

See Appendix 4 for monitoring plan.

12.4 Monitoring of Subjects with Adverse Events

Each subject must be carefully monitored for AEs. This includes clinical laboratory variables. Assessments must be made of the seriousness, intensity and relationship to the administration of the study treatment. After the initial AE/SAE report, the investigator is required to follow up each subject proactively and provide further information as needed to the CHOP IRB and FDA as required.

12.5 Procedures to be Followed in the Event of Abnormal Laboratory Test Values

In the event of unexplained abnormal laboratory test values, the tests should be repeated immediately and followed up until they have returned to the normal range and/or an adequate explanation of the abnormality is found.

12.6 Clinical Laboratory Parameters and Abnormal Laboratory Test Results

Clinically significant changes in laboratory parameters (abnormalities), in the judgment of the Investigator, will be recorded as AEs and appropriate countermeasures taken.

12.7 Abnormal Physical Examination Findings

Clinically significant changes in physical examination findings (abnormalities), in the judgment of the Investigator, will be recorded as AEs and appropriate countermeasures taken.

12.8 Additional Safety Assessments

Safety will be assessed using AEs, observed local and systemic allergic symptoms, physical examinations, including skin reactions, hematology, biochemistry, and vital signs.

Drug accountability will be noted by the field monitor during site visits and at the completion of the trial.

12.9 Treatment of Overdose of Study Medication

There is no experience of overdosing with Viaskin® patches. No specific treatment for overdosing is known. Treatment given to a subject in case of overdosing should be symptomatic and supportive.

Any overdose, with or without associated AEs, in a clinical study must be reported to the local IRB and FDA as required. Overdose will be reported in the eCRF. All reports of overdoses must be filed in the Study Center File. Any AEs associated with the overdose should be reported on relevant AE/SAE sections in the eCRF.

12.10 Procedures in Case of Pregnancy

Pregnancy in itself is not regarded as an AE unless there is a suspicion that an investigational product may have interfered with the effectiveness of a contraceptive medication. However, the outcome of all pregnancies (spontaneous miscarriage, elective termination, normal birth or congenital abnormality) must be followed up and documented even if the subject was discontinued from the study.

All reports of congenital abnormalities/birth defects are SAEs. Spontaneous miscarriages should also be reported and handled as SAEs. Elective abortions without complications should not be handled as AEs. All pregnancies and outcomes of pregnancy must be reported to IRB.

12.11 Adverse Events of Special Interest

AEs of special interest in this study include Grade 4 local skin reactions upon application and removal of the Viaskin®. Skin reactions at the site of Viaskin® Patch application will be examined at the time points specified at each visit and graded according to Section 11.13 (Table 5). Specifically, the appearance of any vesicle(s) or ulcerative skin lesion(s) or any other significant skin lesion which could potentially lead to skin barrier disruption at sites of Viaskin® applications will be considered AEs of special interest. Any occurrence of systemic (or distant) allergic reaction related to Viaskin® Milk application will also be considered an AE of special interest.

13. DATA MANAGEMENT AND STATISTICAL ANALYSIS

The data management and statistical analysis of this study will be performed by an external BDMC (Biostatistics and Data management Core) at CHOP managed by Westat.

13.1 Data Management

An eCRF will be used for the current study, and a data management plan will be prepared by the BDMC (Biostatistics and Data management Core) at CHOP managed by Westat.

Previous and concomitant medications will be coded using the latest available World Health Organization (WHO) Drug Reference Dictionary. Coexistent diseases and AEs will be coded using Medical Dictionary for Regulatory Activities (MedDRA).

When the database has been declared to be complete and accurate, the database will be locked. Any changes to the database after that time can only be made by written agreement between the investigator and the Westat BioStat unit.

13.2 Sample Size Estimation

This is a pilot study in which we aim to identify efficacy of the Viaskin® Milk treatment. Sample size is based on projected subject volume. If efficacy is shown, our pilot data could be used to perform a power analysis for a larger study.

We will recruit 38 subjects and plan to have approximately 22 evaluable subjects with milk-induced EoE confirmed by endoscopy and biopsy.

A total sample size of 22 evaluable subjects (16 subjects in the active Viaskin® Milk group and 6 subjects in the placebo group) will achieve 90% power to detect a difference of 40 in mean maximum eosinophil counts between the two treatment groups (mean maximum eosinophil counts of 10 and 50 in Viaskin® Milk and in placebo, respectively) assuming that a common standard deviation is 20 using a two group *t*-test with a two-sided significance level of 0.05.

Approximately 22 subjects will be randomized to obtain 18 completed subjects with 10% drop-out.

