 17. Past or current disease(s), which in the opinion of the Principal Investigator, may affect the subject's participation in this study, including but not limited to active autoimmune disorders, immunodeficiency, malignancy, uncontrolled diseases (hypertension, psychiatric (especially anxiety), cardiac), or other disorders (e.g., liver, gastrointestinal, kidney, cardiovascular, pulmonary disease, or blood disorders).
 18. Any history of drug or alcohol abuse in the past five years.
 19. Subjects unable to follow the protocol and the protocol requirements.
 20. Participation in another clinical intervention study in the three months prior to Visit 1.
 21. Subjects on any experimental drugs or treatments.

NUMBER OF SUBJECTS: Approximately 22 subjects (16 subjects in the active Viaskin® Milk group and 6 subjects in the placebo group) will be randomized to obtain 18 completed subjects. This sample size will have 90% power to detect a difference of 40 in mean maximum eosinophil counts between the subjects receiving Viaskin® Milk (mean maximum eosinophil count of 10) and the subjects on placebo (mean maximum eosinophil count of 50) assuming a common standard deviation of 20 using a two group *t*-test with a two-sided significance level of 0.05.

STUDY TREATMENT(S): Viaskin Milk will be administered using the Viaskin® epicutaneous delivery system. Viaskin® Milk contains a dry deposit of natural milk protein formulated without adjuvant. The inner part of the Viaskin® Milk has a diameter of 24 mm (4.5 cm² surface area). In this inner part, the milk allergen extract is deposited by electrospraying the liquid milk protein formulation, which dries instantly. The outer adhesive part of the Viaskin® is composed of a 3 mm wide band of adhesive foam to stick to the skin. The outer part of the Viaskin® Milk has a diameter of 30 mm.

Subjects will be randomized to receive Viaskin® with milk protein (500 µg of milk proteins) or placebo during the first year in the study. The placebo treatment will consist of a similar formulation, but will be devoid of milk proteins. During the second year in the study (after third upper endoscopy), all subjects will receive open-label Viaskin Milk 500 µg. Once applied to the skin, the hypoallergenic adhesive film TegaDerm® must be used to cover the Viaskin® to prevent it from coming off. Other dressings could also be used as an alternative to TegaDerm® as allowed by the Principal Investigator.

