8.3 Study Duration

The planned duration of the clinical study is approximately 3 years (Start-up + Screening period + Treatment period + Closeout). Subject participation will be approximately 2 years (including up to 3 months and 2 weeks screening period, 11 months treatment period, 11 month open label extension and 2-week follow-up). Recruitment into the study will stop when approximately 22 subjects have been randomized to treatment. The study will be stopped when the last subject receiving the double-blind treatment completes the study or when the last ongoing subject has discontinued treatment, whichever occurs first.

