#### **2.4.2 Randomization and replacement**

Approximately 22 eligible subjects to obtain 18 completed subjects will be randomized in a 3:1 ratio into two different treatment groups, (1) to receive EPIT with Viaskin® Milk (500 µg of milk proteins) or (2) placebo (16 subjects in the active Viaskin® Milk group and 6 subjects in the placebo group). Subjects who are withdrawn after beginning the treatment phase of the study will not be replaced. However, sufficient subjects will be included to ensure the minimum sample size.

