#### **2.4.3 Study duration**

The planned duration of the clinical study is approximately 3 years (Start-up + Screening period + Treatment period + Closeout). Subject participation will be approximately 2 years (including up to 3 months and 2 weeks for the screening period; 11 months for the treatment period; 11 months for open label extension; and a 2-week follow-up visit). Recruitment into the study will stop when approximately 22 subjects have been

randomized to treatment. The study will be stopped when the last subject receiving the double-blind treatment completes the study or when the last ongoing subject has discontinued treatment, whichever occurs first.

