#### **3.2 Sample size determination and power calculation**

The primary objective of this study is to determine whether mean maximum eosinophil counts is different in the subjects on the Viaskin Milk group compared to those on the placebo group. This is a pilot study in which we aim to identify efficacy of the Viaskin® Milk treatment. Sample size is based on projected subject volume. If efficacy is shown, our pilot data could be used to perform a power analysis for a larger study. We will recruit 38 subjects and plan to have 22 evaluable subjects with milk-induced EoE confirmed by endoscopy and biopsy. Approximately 20 subjects (15 subjects in the active Viaskin® Milk group and 5 subjects in the placebo group) will be randomized to two treatment groups to obtain 18 completed subjects assuming 10% dropout rate. This sample size will have 90% power to detect a difference of 40 in mean maximum eosinophil counts between the subjects receiving Viaskin® milk (mean maximum eosinophil count of 10) and the subjects on placebo (mean maximum

eosinophil count of 50) assuming a common standard deviation of 20 using a two group *t*-test with a two-sided significance level of 0.05.

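### The stated 90% power, 10% drop-out and number randomised do not fit together: 16/6 gives 97.8% power, 22 to 18 is an 18.2% loss, and the SAP randomises both 20 and 22

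*Protocol*

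**What the plan says.** Four places describe the sample size.

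- **Protocol 13.2** recruits 38 to have about 22 evaluable subjects, split 16 active and 6 placebo. Of these 22 it says: "6 subjects in the placebo group) will achieve 90% power to detect a difference of 40 in mean maximum eosinophil counts". The inputs are means of 10 and 50, a common SD of 20, and a two-group t-test at two-sided 0.05. It closes with: "Approximately 22 subjects will be randomized to obtain 18 completed subjects with 10% drop-out".
- **Protocol synopsis** also has about 22 (16/6), "randomized to obtain 18 completed subjects. This sample size will have 90% power to detect a difference of 40". It gives no drop-out rate.
- **SAP 2.4.2**: "Approximately 22 eligible subjects to obtain 18 completed subjects will be randomized in a 3:1 ratio", again split 16/6.
- **SAP 3.2** plans 22 evaluable subjects, but continues: "Approximately 20 subjects (15 subjects in the active Viaskin® Milk group and 5 subjects in the placebo group) will be randomized". The stated aim is "to obtain 18 completed subjects assuming 10% dropout rate". It then claims 90% power on the same inputs.

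The recruitment stop is the same in both documents. Protocol 8.3: "Recruitment into the study will stop when approximately 22 subjects have been randomized to treatment". SAP 2.4.3: "Recruitment into the study will stop when approximately 22 subjects have been" randomised.

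**The concern.** Three figures conflict.

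1. A standardised difference of 40/20 = 2 is very large. With 16 and 6 subjects one expects power well above 90%.
2. A 10% loss does not take 22 subjects to 18.
3. The SAP gives two numbers to randomise, and SAP 3.2 plans more evaluable subjects (22) than it randomises (20).

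In the synopsis and SAP 3.2 the power sentence refers back to the sample size just after naming 18 completers, so the 90% could belong to either the randomised or the completed number. Protocol 8.2 describes the pilot as powered to show significance against placebo, so the power statement carries a design claim. Protocol 8.4.3.4 and SAP 2.4.2 also promise enough subjects to secure the minimum sample size. That promise cannot be checked while the minimum might be 22, 20 or 18.

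**Working it through.** **Inputs** (Protocol 13.2, the same in SAP 3.2): difference 50 − 10 = 40; common SD 20; two-sided α = 0.05; two-group t-test.

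**Power formula** (exact, pooled t-test): df = n1 + n2 − 2; noncentrality = 40 / (20·√(1/n1 + 1/n2)) = 2·√(n1·n2/(n1 + n2)); power is the noncentral-t probability beyond ± the critical value.

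**The plan's own figure, 16/6.** df = 20, critical t = 2.086, noncentrality = 2·√(96/22) = 4.178. Power = 97.8%, against 90% stated. Variants at 16/6 do not recover 90% either: normal approximation 98.7%, one-sided 0.05 99.2%, unequal-variance (Welch) t-test by simulation about 95%. To get 90% at 16/6 the SD would have to be about 24.5, or the difference about 32.6. Neither is in the documents.

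**Other numbers in the plan, same formula:**

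| Total | Split | Noncentrality | Power |
|---|---|---|---|
| 22 | 16/6 | 4.178 | 97.8% |
| 20 | 14/6 | 4.099 | 97.2% |
| 20 | 15/5 | 3.873 | 95.5% |
| 20 | 16/4 | 3.578 | 92.2% |
| 18 | 12/6 | 4.000 | 96.3% |
| 18 | 13/5 | 3.801 | 94.6% |
| 18 | 14/4 | 3.528 | 91.1% |
| 18 | 15/3 | 3.162 | 84.3% |
| 18 | 16/2 | 2.667 | 70.7% |

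**Drop-out.**

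- Protocol 13.2: (22 − 18)/22 = 18.2%. A 10% loss would leave 22 × 0.9 = 19.8.
- SAP 3.2: (20 − 18)/20 = 10.0%, so the 10% fits this chain only.

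**Which split of 18 is likely.** No document gives it. Assume 4 of the 22 (16/6) drop out regardless of arm. The probabilities are then 12/6 24.9%, 13/5 45.9%, 14/4 24.6%, 15/3 4.4% and 16/2 0.2%. The first three sum to 95.4%, with power from 91.1% to 96.3%. Average power over all five splits is 93.7%.

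**The case against.** The best case against giving this weight is that nothing in the design depends on the 90%. Both documents say the size rests on projected subject volume, the counts are approximate, and 20 against 22 is two subjects. In the synopsis and SAP 3.2 the 90% can be read as referring to the 18 completers, where it is a fair rounding down (91.1% at 14/4). Evaluable probably means EoE confirmed before randomisation, since Protocol 13.2 ties the word to confirmation by endoscopy and biopsy among 38 recruited. Printing 97.8% beside 22 would also advertise an optimistic figure that only 18 expected completers would have to live up to.

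Much of this stands as a limit on importance. It does not remove the errors. Protocol 13.2 attaches 90% to 16/6 without ambiguity, and being approximate does not turn 18.2% into 10%. The SAP is based on protocol version 7.0 while the current protocol is 8.0, but sections 2.4.2 and 3.2 conflict within the same SAP. The point about 97.8% is a good reason to prefer tying power to completers.

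**Conclusion.** The concern holds on all three parts. Power at 16/6 is understated by about 8 percentage points (97.8% against 90%). The stated drop-out is little more than half the implied one (10% against 18.2%). SAP 3.2 contradicts SAP 2.4.2 and the recruitment stop in both documents.

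The power error is conservative. On the stated inputs and the pooled t-test, power exceeds 90% at 22 (16/6), at 20 (15/5), and at 18 split 13/5 or 14/4. It falls below 90% only at 15/3 or 16/2, together about 4.6% likely if drop-out is independent of arm.

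Two cautions apply. The margin depends on pooling the variance, as the assumption of a common SD implies; a Welch test would give about 90% at 15/5, 89% at 13/5 and 78% at 14/4. The origin of the 90% also cannot be settled. With the pooled test the nearest of the planned numbers is 18 at 14/4, but that is an inference. This should be corrected before the text passes into the study report; it is not a reason to change enrolment.

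**What to change.** Use one chain in the synopsis, Protocol 13.2, SAP 2.4.2 and SAP 3.2:

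- **Randomised:** 22 (16/6), replacing 20 (15/5) in SAP 3.2. Note that 16/6 is 2.67:1, an approximation to the stated 3:1.
- **Drop-out and completers:** the sponsor states which was intended. Either 10% with about 20 completers (power 95.5% at 15/5; 92.2% to 97.2% for 16/4 to 14/6), or about 18% with 18 completers (91.1% to 94.6% for 14/4 to 13/5).
- **Power:** preferably attach it to the expected completers and give the assumed split. If a figure stays beside 22 evaluable, it should be 97.8%.
- **Evaluable:** say whether it means EoE confirmed before randomisation or analysed at Visit 10.

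The cost is a text correction in two documents, with no extra patients and no change to conduct or analysis.
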